9.2. Clinical Laboratory Evaluations

Laboratory evaluations (including hematology, serum chemistry, and urinalysis) will be collected at the screening visit (within 30 days prior to Day 1), and a summary of screening information will be provided by treatment arm and by total.

9.3.Vital Sign Measurements

Vital sign data will be summarized at each visit by treatment arm. Changes from baseline to each scheduled post-baseline visit will be presented as well.

9.4. Physical Examination

During physical examinations, body systems will be assessed as normal, abnormal, or not examined at each scheduled visit, and the percentage of subjects with abnormal physical examination findings at each time point will be summarized by body system and by treatment arm.

9.5.Electrocardiogram

A single 12-lead electrocardiogram (ECG) will be performed at Screening after the subject has been in a supine position for at least 10 minutes. ECG results will be summarized by treatment arm and by total, for interpretation results including Normal, Abnormal Not Clinically Significant, Abnormal Clinically Significant, and Not Done.

10. Interim Analysis

No formal interim analyses will be performed for this study. For reasons of futility (early evidence of poor efficacy of VGX-3100) or safety issues, the Data and Safety Monitoring Board (DSMB) could recommend stopping enrollment at any time. The type I error of 0.05 will not be adjusted for possible early stopping due to futility.

Group-level unblinded (VGX-3100, Placebo) summaries and analyses may be produced once the primary endpoint Week 36 visit data are completed for all subjects; subject-level blinding will be maintained. The summaries and analyses will allow the Sponsor to have results with respect to the primary endpoint and key safety outcomes on which to make decisions regarding the VGX-3100 program while awaiting final database lock. The planned set of summaries and analyses is comprised of a) the primary composite endpoint of histopathologic regression and virologic clearance and b) adverse events of progression to cervical cancer. Both will be performed on the biomarker-positive set of subjects and on all subjects. None of these summaries or analyses will be provided if the total count of subjects who experience the event of interest is greater than 0 and the count for any treatment group relative to this total count is less than 3% for a given summary/analysis. The group-level unblinded (VGX-3100, Placebo) production of the summaries and analyses will not include anyone directly involved with the trial or any additional unblinded personnel; only the external Contract Research Organization (CRO), PPD, which has already been providing unblinded summaries for the Data Safety Monitoring Board, will be utilized. Thus, the trial will remain blinded with respect to subject treatment assignment throughout the trial. The type I error of 0.05 will not be adjusted for this procedure.

11. Changes in the Planned Analysis

The protocol stated that the percentage of subjects with abnormal medical history findings by body system will be summarized for biomarker-positive subjects and all subjects. However, these summaries will not be included because body system for medical history findings were not coded in the data.

12. References

- A Prospective, Randomized, Double-Blind, Placebo-Controlled Phase 3 Study of VGX-3100 Delivered Intramuscularly Followed by Electroporation with Cellectra[™] 5PSP for the Treatment of HPV-16 And/Or HPV-18 Related High Grade Squamous Intraepithelial Lesion (HSIL) of the Cervix, Version 3.0, 23 September 2016.
- 2. Centers for Disease C, Prevention. Human papillomavirus-associated cancers United States, 2004-2008. MMWR Morb Mortal Wkly Rep 2012,61:258-261.
- 3. Future II Study Group. Supplementary Material: Quadrivalent vaccine against human papillomavirus to prevent high-grade cervical lesions. N Engl J Med 2007,356:1915-1927.

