8.4 ANALYSIS POPULATIONS/DATASETS

Analysis populations will include:

The intention to treat (ITT) population includes all subjects who are randomized. Subjects in this sample will be grouped to treatment arms as randomized. Analysis of the ITT biomarker-positive population will be primary for the analysis of efficacy in this study.

The modified intention to treat (mITT) population includes all subjects who receive at least one dose of Study Treatment and who have the analysis endpoint of interest. Subjects in this sample will be grouped to treatment arms as randomized. Analysis of the mITT population will be considered supportive for the corresponding ITT population for the analysis of efficacy.

The per-protocol (PP) population comprises subjects who receive all doses of Study Treatments and have no protocol violations and who have the analysis endpoint of interest. Subjects in this sample will be grouped to treatment arms as randomized. Analyses on the PP population will be considered supportive of

Version Date: 01Jun2022

CONFIDENTIAL

Version 4.1

Page 72 of 87

the corresponding ITT population for the analysis of efficacy. Subjects excluded from the PP population will be identified and documented prior to unblinding of the study database.

The safety analysis set includes all subjects who receive at least one does of Study Treatment. Subjects will be analyzed as to the treatment received.

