4.3.3. Per Protocol

The per-protocol (PP) population comprises subjects who receive all doses of Study Treatments and have no protocol violations and who have the analysis endpoint of interest. Subjects in this sample will be grouped to treatment arms as randomized. Analyses on the PP population will be considered supportive of the corresponding ITT population for the analysis of efficacy. Additional analyses on the PP population will utilize the Week 36 timeframe result regardless of any procedure performed before the Week 36 timeframe, thus serving as sensitivity analyses regarding early intervention. Subjects excluded from the PP population will be identified and documented prior to unblinding of the study database.

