4.5. Baseline Definition

Baseline is defined as the last measurement prior to the first treatment administration. If the first treatment date is not available, the last measurement before or on the randomization date will be used.

4.6.Study Day

The day of the first study treatment is defined as Day 1. Study day for a particular event date is calculated as (Date of event – Date of Day 1 + 1) if the event occurs on or after Day 1, or (Date of event – Date of Day 1) if the event occurs prior to Day 1, and the study day of any event prior to the first study treatment will be a negative number. Duration of an event will be calculated as (Event end date – Event start date +1).

5. Subject Disposition

5.1.Disposition

Number and percentage of subjects in each analysis population will be summarized by treatment arm and total.

Additionally, the number and percentage of subjects who received each dose, complete all electroporation/study treatments, completed all study visits, discontinued study treatment, and early withdraw from the study will be presented. The reasons for study treatment discontinuation and early withdrawal from study will also be summarized.

A disposition table of subjects by country and site, and by treatment will also be summarized.

Summaries will be performed on the baseline biomarker-positive subjects and on all subjects (regardless of biomarker status) separately. Disposition listings will flag all subjects who are baseline biomarker positive.

5.2.Protocol Deviations

Deviations from the protocol including violations of inclusion/exclusion criteria will be identified in cooperation with the sponsor. All subjects excluded from the PP population will also be identified. These identifications will be defined prior to database lock.

Protocol deviations are to be mainly classified as a ICH-GCP/non-ICH GCP deviation as well as a Covid/Non-Covid Related deviation. In addition, the number and percentage of subjects with at least one protocol deviation, 1 deviation, 2 deviations, >2 deviations will be summarized. Subjects excluded from the PP population will be presented separately.

6. Demographics and Baseline Characteristics

6.1.Demographics

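### Does the optional arm-level release before database lock leave the per-protocol exclusions, or the Week 36 endpoint, open to influence by the result?

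*SAP*

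**What the plan says.** SAP section 10, Interim Analysis, plans no formal interim analysis but permits an early output: "Group-level unblinded (VGX-3100, Placebo) summaries and analyses may be produced once the primary endpoint Week 36 visit data are completed for all subjects". It covers the primary composite endpoint and progression to cervical cancer, in biomarker-positive women and in all women. Its purpose is to let the sponsor "make decisions regarding the VGX-3100 program while awaiting final database lock". Only the external CRO that already served the DSMB produces it, subject-level blinding is kept, and alpha is not adjusted. Protocol 8.5.6 carries the same text.

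SAP 5.2, Protocol Deviations, says that deviations "will be identified in cooperation with the sponsor". It continues: "All subjects excluded from the PP population will also be identified", and "These identifications will be defined prior to database lock".

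SAP 4.3.3 words the deadline differently: "Subjects excluded from the PP population will be identified and documented prior to unblinding of the study database". Protocol 8.4 agrees with 4.3.3: PP exclusions "will be identified and documented prior to unblinding of the study database". PP members must receive all doses, and must "have no protocol violations and who have the analysis endpoint of interest". Both documents call the PP analyses supportive of ITT. ITT in biomarker-positive women is primary (SAP 4.3.1, Protocol 8.4).

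**The concern.** Taken literally, SAP 5.2 and SAP 10 allow an awkward order of events. The sponsor receives the arm-level primary result, and afterwards helps decide who leaves the PP population. Time for this exists, because the Week 40 visit (± 2 weeks) follows Week 36. Neither document lists which deviations count as violations, so exclusion involves judgement. SAP 10 restricts who produces the output but does not say which sponsor staff receive it.

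The trigger raises a second doubt. It asks for Week 36 data that are complete, and names no freeze. Under SAP 8.1.1 response depends on dates: a biopsy or excision before Day 238 makes a woman a non-responder, and the HPV result used is the latest one on or before the histology date. If such dates were corrected after the release, the final primary result could differ from the one already seen.

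At stake would be the credibility of the PP analyses (including the early-intervention sensitivity analysis) and, on the second doubt, of the primary endpoint data.

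**Working it through.** **1. The deadlines side by side.** SAP 5.2 says before lock; SAP 4.3.3 and Protocol 8.4 say before unblinding of the database. Both bind and both can be met, so the earlier one governs.
- If the group-level release counts as unblinding, PP exclusions must precede it and there is no gap.
- If it does not count, exclusions may follow it, but without subject codes. Steps 3 to 5 size that case.

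**2. The plan's own figure.** Inputs from SAP 4.1: 198 randomised 2:1, 33% biomarker-positive, response 66% vs 15%. 198 × 0.33 = 65.3, taken as 44 vs 22. Power is 99.3% by normal approximation, 98.8% by exact enumeration of the Miettinen–Nurminen test, and 98.5% averaged over a random biomarker-positive count. All agree with the stated figure of over 90%.

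**3. PP exclusions without codes, planning rates.** Counts: 29/44 vs 3/22, difference 0.6591 - 0.1364 = 0.5227. Responders 29 + 3 = 32; non-responders 15 + 19 = 34. The planning rates count missing as failure, so as PP counts these are illustrative.
- One random non-responder out: 15/34 × (29/43 - 29/44) - 19/34 × (3/21 - 3/22) = +0.0031.
- One random responder out: 29/32 × (28/43 - 29/44) + 3/32 × (3/22 - 2/21) = -0.0033.
- One of each, averaged over the four outcomes: 0.0000.

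**4. Endpoint corrections without codes, same counts.**
- Non-responder to responder: 15/34 × 1/44 - 19/34 × 1/22 = -0.0154.
- Responder to non-responder: -29/32 × 1/44 + 3/32 × 1/22 = -0.0163.

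Both move towards zero. In an assumed smaller-effect case (16/44 vs 3/22, difference 0.2273) the five shifts, in the same order, are +0.0024, -0.0060, -0.0035, -0.0048 and -0.0120.

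**5. A deliberately borderline case (assumed counts).** Take 18/44 vs 4/22. At a null difference of zero the statistic is z = (pV - pP) / √[p̄(1 - p̄)(1/nV + 1/nP) × N/(N - 1)]. With p̄ = 22/66, z = 0.2273 / 0.1240 = 1.83 and the one-sided p is 0.0335. Removing three VGX-3100 non-responders gives 18/41 vs 4/22 and p = 0.0214. Picking those three by arm needs the codes. Without them, three of the 26 + 18 = 44 non-responders go at random:

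| VGX-3100 women among the three | Probability | One-sided p |
|---|---|---|
| 0 | 0.062 | 0.066 |
| 1 | 0.300 | 0.046 |
| 2 | 0.442 | 0.032 |
| 3 | 0.196 | 0.021 |

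The average p is 0.036, slightly worse than at the start, and the chance of falling below 0.025 is 20%.

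**6. Type I error.** The release comes after all Week 36 data are in, and there is one test with no second chance to reject. The look does not inflate the error rate of that test.

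**The case for a change.** The best case for a change is that the sequence is allowed, the party that may hold the result helps settle the exclusions, and SAP 10 describes the trial as still blinded to subject assignment. That last point suggests the release is not the unblinding meant in 4.3.3. One sentence fixing the order would be cheap, and the order cannot be proved afterwards. As a reading of the text this stands: the term is undefined and the recipients are not named.

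The codes are also not perfectly opaque. Protocol 3.5 reports erythema in 78% vs 57% in HPV-003. If those rates held here and were unrelated to response, the chance that a non-responder with erythema is on VGX-3100 would be (15 × 78) / (15 × 78 + 19 × 57) = 1170/2253 = 52%, against 15/34 = 44% without the clue. Excluding her would move the PP difference by 0.519 × 0.0153 - 0.481 × 0.0065 = +0.005, or half a point. The clue is real and weak.

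The doubt about unfrozen data does not stand as a finding. It argues from silence: data complete for all subjects can fairly mean final endpoint data, and data-management procedures are not among the documents. The endpoint leaves little discretion. SAP 8.1.1 takes the first tissue on or after Day 238, the worst grade on that day, and the latest HPV result up to that date. At least two pathologists read each specimen independently and blinded (Protocol 12.3), and a central laboratory reads the Pap smears (Protocol 6.4.12). A freeze that still admitted logged corrections would also leave genuine errors to be put right, as they should be.

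**Conclusion.** No change to the plan follows. SAP 5.2 and SAP 4.3.3 word one deadline in two ways, and a study team can satisfy both by closing the PP list before the CRO produces any group-level output. If it did not, the exposure would be confined to supportive analyses, at about 0.3 points per exclusion at the planning rates and up to 0.6 in the smaller-effect case, with a sign that depends on the response of the woman excluded. The primary ITT result is untouched by PP membership, and corrections made without codes would on average weaken it.

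This rests on three assumptions: about 66 biomarker-positive women split 44 to 22, subject codes that stay closed as SAP 10 requires, and response counts near the planning rates or the assumed smaller-effect case. The borderline example shows that a few women can matter when p is close to 0.025. Even there, exclusions made without codes do not favour VGX-3100 on average. The issue is one of documentation; no bias is shown.

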13.1. Schedule of Events

		Weeks										
Tests	Screening* (-10 weeks to -1 Day from date of biopsy)	Day 0	8-14 days post Day 0 Phone Call	4 (± 4 days)	8-14 days post Wk 4 Phone Call	8 (± 4 days)	12 (± 4 days)	8-14 days post Wk 12 Phone Call	15 (± 1 week)	28 (± 1 week)	36 (± 1 week)	40 (± 2 weeks)
Informed consent	Х											
Medical History	х											
Demographics	Х											
Socio-behavioral ^a	Х										х	x
Inclusion / Exclusion	х	х										
Randomization		х										
Physical exam/assessment b	х	х		Х		х	х		x	х	х	х
Vital signs	X ^c	х		х		х	х		x	х	x	х
Screening safety d	х											
Pregnancy Test ^e	х	х		Х			х		х	х	x	X
HIV Antibody Testing	X q											
Blood immunologic samples ^f	X q	х				х			X g		x	
Cervical Digene swabs ^{i,j}	X q	х							х	х	x	
ThinPrep ^{™ h, i}	X q	х				х			х	х	х	
Colposcopy ^k	X ^{1, q}	х							х	х	х	х
Ectocervical biopsy m	X q										X ⁿ	
Surgical excision ^m											X ⁿ	
OP rinse, vaginal swabs, intra- anal swabs °		х									x	
Inject VGX-3100/Placebo		х		Х			х					
Post treatment assessment		Х	X	Х	Х	Х	Х	X ^p	X			
AE/SAE assessment	Х	Х	X	X	X	Х	Х	X	X	X	X	X
(PDC)		х		х			х					
Review PDC			Х		Х	Х		X ^p				

- a Socio-Behavioral assessments, e.g. self-reported smoking and alcohol history
- b Complete physical examination (PE) mandatory at screening and study discharge (Week 40), otherwise targeted physical assessment as determined by the Investigator or per subject complaints unless signs or symptoms dictate the need for a complete PE;
- c Screening vital signs must include a measured height and weight. Height and weight will be collected on Day 0, Weeks 4 and 12;
- d Screening safety procedures includes 12-Lead ECG, complete blood count (CBC), serum electrolytes,
 blood urea nitrogen (BUN), serum creatinine (Cr), serum Albumin, serum glucose, serum ALT, serum
 CPK and urinalysis performed within 60 days prior to Day 0;
- e For WOCBP, a negative spot urine pregnancy test is required at screening and prior to each study treatment, colposcopy and surgical excision;

Inovio HPV-303 Final SAP v1.2 | VV-TMF-129563 | 1.0

Inovio Pharmaceuticals, Inc. HPV-303

- i Request that the subject abstain from sexual activity and refrain from use of douching or vaginal lubricants/medication for a period of 24 hours prior to cervical specimen collection;
- j Collected prior to the ThinPrep[™] sample;
- k Acetic acid should be applied to lesions before biopsies at colposcopic examinations for the Screening and Week 36 visits;
- 1 Screening colposcopy is optional if adequate colposcopy was performed upon collection of initial biopsy;
- m Screening biopsy of the lesion should be collected as paraffin-embedded cervical tissue, fresh cervical tissue, or H&E slides. In the absence of paraffin-embedded or fresh tissue, unstained slides will be required in addition to H&E slides. Tissue to be analyzed for evidence of histopathologic regression will be obtained at Week 36 visit either by excision (e.g. LEEP, LLETZ, CKC) or by 4 Quadrant Biopsy or 4 Quadrant Biopsy with ECC based upon the assessment at Week 28 of cytology, HR HPV status, and colposcopic findings (See Tables 4 and 5);
- n Slides from biopsy and/or excised tissue must be reviewed by the PAC and residual cervical tissue from screening and/or Week 36 specimen(s) (paraffin blocks or unstained slides) may be used for assessment of as well as HPV testing;
- o Please refer to the Laboratory Manual for specific information regarding biological sample collection
- p Activities at 8 to 14 days Post-Dose 3 phone call may be done at Week 15 if timing overlaps.
- q Results and activities performed as part of the screening process in the HPV-301 trial can be used as qualifying historical information to satisfy screening activities for HPV-303 provided that they were assessed within the required timeframes for HPV-303 screening.

Inovio HPV-303 Final SAP v1.2 | VV-TMF-129563 | 1.0

Inovio Pharmaceuticals, Inc. HPV-303
